## 2. Summary

Tenecteplase in Wake-up Ischaemic Stroke Trial (TWIST) is a randomised-controlled, open-label trial of thrombolytic treatment with tenecteplase for acute ischaemic stroke upon awakening.

The trial aims to answer the following questions:

- Can thrombolytic treatment with tenecteplase given within 4.5 hours of wake-up reduce the risk of poor functional outcome at 3 months?
- Can findings on non-contrast CT and CT angiography (and CT perfusion at selected centres) identify patients who benefit from such treatment, compared to patients without such findings?

Patients are eligible if they have ischaemic stroke causing measurable neurologic deficits, and can be given tenecteplase within 4.5 hours after awakening. Patients will undergo brain CT and CT angiography (if possible) to exclude large infarction or other contraindications to thrombolytic treatment. Non-contrast CT and CT angiography (if possible) will be repeated on day 2.

Patients will be allocated to tenecteplase 0.25 mg/kg as a bolus (maximum dose 25 mg) or to control. The primary effect variable is functional outcome at 3 months, as measured by the modified Rankin Scale (mRS).

The target is to include a total of 600 patients from centres in Norway, Sweden, Denmark, Finland, Estonia, Lithuania, Latvia, Switzerland, New Zealand and the United Kingdom. The sponsor of the trial is University Hospital of North Norway.

## 3. Background and rationale

### 3.1 Introduction

Thrombolytic treatment with recombinant tissue plasminogen activator (rt-PA) given within 4.5 hours of onset improves clinical outcome after ischaemic stroke, despite an increased risk of intracranial haemorrhage. Patients who have new stroke symptoms when they wake up from sleep (“wake-up stroke”) are excluded for such treatment, because the time of stroke onset is unknown. About one in five strokes occur during sleep, and it is unknown whether patients with wake-up stroke will benefit from thrombolytic treatment.

There are reasons to expect that patients with wake-up stroke will benefit from treatment. Several studies have shown that the onset of stroke during sleep is close to awakening, and that patients with wake-up stroke share many clinical and radiological findings with patients with stroke duration less than 4.5 hours. Studies have also shown that thrombolytic treatment is safe in patients with wake-up stroke up to 4.5 hours from wakening, and recently the WAKE-UP trial showed benefit of treatment with alteplase in patients selected based on DWI/FLAIR mismatch on MRI. In a Cochrane systematic review we have identified only one completed, small randomised-controlled trial of only nine patients. Two trials have recently been completed (EXTEND, THAWS,) and one is on-going (WASSABI, see Appendix). All these three trials use alteplase, and all use advanced imaging techniques for selection of patients. We will use a different strategy, and perform a large trial of tenecteplase, using a pragmatic study design, without exclusion of patients based on MRI findings. The trial will be complementary to the other trials, and is planned in advance to be included in our Cochrane meta-analysis of all trials of thrombolytic treatment for wake-up stroke, so that smaller, but still worthwhile effects can be detected that may be missed by the individual trials.

### 3.2 Potential benefits and harms of tenecteplase

#### Pharmacological properties

Tenecteplase is an alteplase molecule that is genetically engineered to have pharmacological advantages over alteplase: it has a 14-fold greater fibrin specificity and a very rapid onset of action compared to alteplase, has a longer half-life, and can be given as a single bolus, whereas alteplase must be given as a continuous infusion over one hour. Tenecteplase also has a smaller effect on plasma fibrinogen levels, which is beneficial for avoidance of intracranial haemorrhage, and weaker pro-thrombotic effects.

**Data from pre-clinical studies**

Animal models have shown that tenecteplase acts faster and more potent than alteplase, and that tenecteplase produces a more rapid and complete recanalisation of occluded arteries. Models have also shown that experimentally induced infarcts were less frequently converted to haemorrhage with tenecteplase than with bio-equivalent doses of alteplase and that the risk peripheral or major haemorrhage and intracranial haemorrhage was equal to or lower than the risk with alteplase.

[figure not shown]
**Data from clinical studies**

Tenecteplase is preferred over alteplase for treatment of myocardial infarction, because it has lower risk of bleeding complications, and because of the pharmacological advantages listed above.

A number of observational studies in patients with ischaemic stroke have shown that, compared to alteplase, tenecteplase is associated with similar or better recanalisation rates and clinical outcomes, and a similar or lower risk of intracranial haemorrhage. These studies have also concluded that the optimal dose of tenecteplase for stroke is 0.25 mg/kg.

[figure not shown]
There has also been three small randomised-controlled trials of tenecteplase vs. alteplase in acute ischaemic stroke. Meta-analysis of these trials with a total of 283 patients have shown that 76/178 patients (43%) patients given tenecteplase (doses ranging from 0.1 to 0.4 mg/kg) achieved good functional outcome (mRS score 0-1), compared to 33/105 patients (31%) patients given alteplase (odds ratio (OR) 1.39, 95% confidence interval (CI) 0.82-2.36, Figure 1).

**Figure 1.** Good functional outcome (mRS score 0-1) at three months

[figure not shown]

There was also a non-significant lower risk of symptomatic intracranial haemorrhage in patients given tenecteplase (Figure 2). The risks were 7/131 (5%) in patients given tenecteplase and 4/56 (7%) in patients given alteplase (OR 0.71, 95% CI 0.11-4.42). ATTEST 2014 did not provide data on symptomatic intracranial haemorrhage.

**Figure 2.** Symptomatic intracranial haemorrhage

There was no significant difference in the risk of death at three months (Figure 3). In total, 24 of the 178 patients (13%) given tenecteplase and 17 of the 123 patients (14%) given alteplase were dead at three months (OR 1.00, 95% CI 0.52-1.95).

**Figure 3. Death of all causes at three months**

Another meta-analysis comparing different doses of tenecteplase concluded that 0.25 mg/kg is the preferred dose over alteplase. There are also observational studies that support this conclusion. Furthermore, an analysis of pooled data for tenecteplase 0.25 mg/kg compared to alteplase 0.9 mg/kg showed trends in favour of tenecteplase. Tenecteplase had higher odds than alteplase for neurological improvement at 24 hours (OR 3.3, 95% CI 1.5-7.2,  $p=0.09$ ), excellent clinical outcomes at three months (OR 1.9, 95% CI 0.8-4.4,  $p=0.3$ ), and good clinical outcomes at three months (OR 1.9, 95% CI 0.5-7.2,  $p=0.4$ ); also, tenecteplase had a lower risk of brain haemorrhage than alteplase (OR 0.3, 95% CI 0.2-1.8,  $p=0.4$ ). Recently, NOR-TEST showed no difference in functional outcome at three months between patients with ischaemic stroke treated with tenecteplase 0.4 mg/kg or alteplase 0.9 mg/kg within 4.5 hours and the EXTEND-IA TNK trial showed that tenecteplase 0.25 mg/kg was superior to alteplase 0.9 mg/kg in improving recanalisation and functional outcome at three months when given within 4.5 hours and prior to intra-arterial intervention. Other trials of tenecteplase in patients with acute ischaemic stroke are ongoing: TASTE, TEMPO-2 and ATTEST2.

### Conclusion: Potential benefits and harms of tenecteplase

The bolus administration and the very rapid onset of action makes tenecteplase an attractive option for patients with wake-up stroke, because the time to recanalisation of an occluded cerebral artery can be reduced by up to one hour, compared to alteplase. Available data from pharmacological in-vitro studies, pre-clinical studies and clinical studies also indicate that tenecteplase 0.25 mg/kg is at least as safe and at least as effective as alteplase for the treatment of acute ischaemic stroke. The favourable profile of tenecteplase seen in these studies and in studies of acute myocardial infarction, in combination with the pharmacological characteristics and advantages of bolus administration, provides a good rationale for testing tenecteplase in patients with wake-up stroke.

### 3.3 Multi-modal CT for the selection of patients to thrombolytic therapy

The WAKE-UP trial and three other trials of thrombolytic treatment for wake-up stroke use/used advanced imaging techniques for selection of patients. Two trials (WASSABI and EXTEND) use CT or MRI perfusion techniques to identify patients with ischaemic penumbra. The penumbra is an area of ischaemic, but still viable brain tissue surrounding the core of a cerebral infarction, which is assumed to be salvageable if blood flow can be promptly restored. The WAKE-UP trial and the THAWS used DWI/FLAIR mismatch on MRI to select patients. Infarct changes on DWI are thought to represent alterations to water diffusion and can be visualised within minutes of onset. Infarct changes on FLAIR are thought to represent cytotoxic oedema and cannot be identified until a few hours after onset. Findings suggestive of ischaemic stroke on DWI, but absence of such findings on FLAIR (DWI/FLAIR mismatch), may therefore identify patients with a short time since onset of cerebral infarction.

Demonstration of penumbra or DWI/FLAIR mismatch identifies patients with a good prognosis, but it does not necessarily identify patients with a better response to thrombolytic treatment than other patients. Only one randomised-controlled trial (MR RESCUE, of intra-arterial interventions) has examined the value of advanced imaging for patient selection, but did not find a better effect of therapy in patients with penumbra, than in patients without penumbra.

On the contrary, there is a risk that selection of patients based on such techniques will exclude patients from receiving an effective treatment. First, it is possible that patients without these specific radiological findings benefit equally well as those who are selected for participation in these trials, as indicated in a recent study. Second, the techniques are far from perfect in characterising patients, for example, DWI/FLAIR mismatch can be absent in as many as 40% of patients with known stroke duration of less than three hours. Third, these MRI techniques are time-consuming and are not available in the emergency setting in many hospitals, which means that time to thrombolytic treatment will be increased, and that some patients will be denied thrombolytic treatment altogether.

We will therefore base patient inclusion on wider and more pragmatic criteria, such as time since wake-up in combination with accepted CT exclusion criteria. Inclusion based on wider criteria will avoid excluding a large number of patients that might benefit from treatment. This will make the results applicable to patients that are encountered in everyday clinical practice, and will dramatically increase the proportion of stroke patients who can be treated. Patient can be included based on non-contrast CT alone, but CT angiography can be routinely done in many hospitals, can be done without significant delay, and can give information that will help in the selection of patients with wake-up stroke for thrombolytic treatment.

## **4. Trial design, questions, and hypotheses**

### **4.1 Trial design**

Randomised-controlled, open-label trial of tenecteplase in patients with acute ischaemic stroke upon awakening.

### **4.2 Study questions and objectives**

The objectives of the trial is to answer the following questions, for patients who have an acute ischaemic stroke upon awakening:

- Can thrombolytic treatment with tenecteplase given within 4.5 hours of wake-up reduce the risk of poor functional outcome at 3 months?
- Can findings on non-contrast CT and CT angiography (and CT perfusion at selected centres) identify patients who benefit from such treatment, compared to patients without such findings?

### **4.3 Hypotheses**

- Thrombolytic treatment with tenecteplase will reduce the risk of poor functional outcome at 3 months. For details about size of effect, see Statistical calculations, below.
- CT angiography and CT perfusion identifies patients who benefits more from tenecteplase than other patients

## **5. Study population**

Patients with acute ischaemic stroke upon awakening who can be given treatment within 4.5 hours after awakening.

### **5.1 Inclusion criteria**

- Stroke symptoms on awakening that were not present before sleep
- Clinical diagnosis of stroke with limb weakness with NIHSS score  $\geq 3$ , or dysphasia
- Treatment with tenecteplase is possible within 4.5 hours of awakening
- Written consent from the patient, non-written consent from the patient (witnessed by non-participating health care personnel), or written consent from the nearest family member

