## 6. Patient screening

### 6.1 Patient screening

All patients who are admitted with new stroke symptoms on awakening should be screened for inclusion into the trial. Patients will be evaluated for vital signs, physical examination, neurological status (NIHSS), ECG and CT with CT angiography (section 6.2). Routine blood tests will include blood glucose and prothrombin time/INR\*, aPTT\*, TT and/or eucarin clotting time if it is suspected the patient is taking direct thrombin inhibitors or direct factor Xa inhibitors.

\*Although it is desirable to know the results of these tests before giving intravenous tenecteplase, fibrinolytic therapy should not be delayed while awaiting the results unless (1) there is clinical suspicion of a bleeding abnormality or thrombocytopenia, (2) the patient has received heparin or warfarin within 48 hours, or (3) the patient has received other anticoagulants/direct thrombin inhibitors or direct factor Xa inhibitors.

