## **6.2 Non-contrast CT and CT angiography for patient screening before randomisation**

All patients should be screened with non-contrast CT, and CT angiography should be performed, if possible. Findings on non-contrast CT shall only be used to exclude patients who are unlikely to benefit from treatment (See Exclusion criteria in Section 5). If other, advanced imaging examinations are used (see sections 6.3 and 6.4, below), findings on such examinations shall not influence the decision to include the patient, unless the results of such imaging show that the patient should or should not receive thrombolytic treatment, in the opinion of the investigator.

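### The 4.5-hour window runs only from awakening, so a short sleeper whose onset is certainly within 4.5 hours of treatment can be randomised to a control arm that bars thrombolysis

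*Protocol*

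**What the plan says.** Protocol section 5 defines the population as "Patients with acute ischaemic stroke upon awakening who can be given treatment within 4.5 hours after awakening". Section 5.1 turns this into two timing criteria: "Stroke symptoms on awakening that were not present before sleep" and "Treatment with tenecteplase is possible within 4.5 hours of awakening". Neither sets a minimum length of sleep or refers to the time last well. The exclusions in section 5.2 cover severity, CT findings, bleeding risk, blood pressure, glucose, pregnancy, prior disability and follow-up. None concerns the time last free of symptoms or an existing indication for thrombolysis. The older protocol version, in the combined document, has the same gap.

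The awakening clock is a deliberate choice. Section 3.3 bases inclusion on criteria such as "time since wake-up in combination with accepted CT exclusion criteria", in order to avoid selecting patients by MRI or perfusion imaging. Section 6.1 adds that "All patients who are admitted with new stroke symptoms on awakening should be screened for inclusion into the trial".

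Section 8.2 forbids thrombolytic drugs of every kind in the control arm. Section 8.3 leaves intra-arterial treatment open to both arms, but only for proximal occlusion.

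**The concern.** Section 3.1 gives both the evidence and the reason for a control arm without thrombolysis. It states that rt-PA "given within 4.5 hours of onset improves clinical outcome after ischaemic stroke", and that patients with wake-up stroke "are excluded for such treatment, because the time of stroke onset is unknown". The second statement is what makes it acceptable to randomise against no thrombolysis.

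That reason does not apply to someone who slept briefly and reached hospital quickly. The exact onset is still unknown, but its earliest possible time is the last symptom-free moment, and that moment lies inside the window the protocol calls beneficial. Read literally, the criteria admit this patient to a trial in which half of those randomised are denied thrombolysis. The rationale in section 3.3 argues against excluding patients through advanced imaging. It does not discuss patients whose timing already falls inside the established window.

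At stake is the care of the individual patient, not the validity of the trial result.

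**Working it through.** The plan gives no figure on this point, so the check is the timing logic set against the text.

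**Inputs.** Limit of 4.5 hours from awakening to possible treatment (section 5.1). Benefit of rt-PA up to 4.5 hours from onset (section 3.1). Sleep duration S and wake-to-treatment time W are illustrative, because the documents give no data on either.

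**Formula.** Symptoms were absent before sleep, so onset cannot precede the start of sleep. The longest possible onset-to-treatment time is therefore S + W. The protocol requires only W ≤ 4.5 h. Onset is certainly inside 4.5 h when S + W < 4.5, that is, when W < 4.5 − S.

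| Sleep S (h) | Affected if treatable within W (h) of waking |
|---|---|
| 1 | 4.5 − 1 = 3.5 |
| 2 | 4.5 − 2 = 2.5 |
| 3 | 4.5 − 3 = 1.5 |
| 4 | 4.5 − 4 = 0.5 |
| 4.5 or more | none |

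**Example.** Well at 04:00, awake with symptoms at 06:00, so S = 2 h. The trial clock runs to 06:00 + 4.5 h = 10:30. The clock from last well runs to 04:00 + 4.5 h = 08:30. If treatment is possible before 08:30, onset is certainly within 4.5 h. Between 08:30 and 10:30 the patient is still eligible and onset is uncertain, which is the situation the trial is meant for.

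**Contrast.** With S = 7 h and W = 2 h the longest possible interval is 9 h, so a normal night's sleep is never caught.

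**Does another provision close the gap?**
- Section 6.1 sends these patients to screening. It does not oblige anyone to enrol them, but it does not divert them either.
- Section 6.2 leaves room for judgement "unless the results of such imaging show that the patient should or should not receive thrombolytic treatment, in the opinion of the investigator". That discretion rests on imaging findings, not on time last well.
- Section 7.1 requires consent, which is a safeguard. It does not tell staff that this group may already have an indication.
- Section 8.3 helps controls with a proximal occlusion, but not the others.
- Section 9 asks for guideline-based care at the clinician's discretion during follow-up. The specific prohibition in section 8.2 is the more natural guide for a control patient.
- Section 12.7 has the central system check eligibility, but no stated criterion gives it this rule to apply. The randomisation form is not in the documents.

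**Sample size, for completeness.** The stated 600 reproduces: the Whitehead proportional-odds formula with odds ratio 1.50, 80% power, two-sided 5% and the section 11.1 control distribution gives 601. The point does not depend on it.

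**The case against.** The best case on the other side has four parts.

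*The intended scope is clear.* Section 3.1 frames the target group as people left untreated because onset is unknown, so a short sleeper with bounded onset is implicitly outside it. That is a fair reading of the intention, but section 3.1 describes wake-up stroke by symptoms on waking, with no limit on sleep length, and the criteria that sites apply say nothing more.

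*Nobody is told to withhold treatment.* A reader might infer that the protocol directs clinicians to deny these patients an established therapy. The documents do not support that. Screening is not enrolment, consent is required, and a clinician may treat instead of randomising. What remains is that no line says so for this group.

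*Harm needs a long chain.* A short sleep, fast arrival, all other criteria met, a decision to randomise, consent, and then allocation to control must all occur, and the documents give no frequency for any of them except the 1:1 allocation. This stands, and it keeps the point minor.

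*Local rules are unknown.* The documents do not set out how each country treats patients by time last well, and the separate operating procedures are not available. This also stands, and the exclusion should therefore refer to local standard care.

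**Conclusion.** The gap is real and the point is minor. As written, the criteria allow a patient whose onset is certainly within 4.5 hours of possible treatment to be randomised to an arm without thrombolysis, although the protocol's reason for non-treatment does not hold for that patient. The affected group is exactly those with S + W < 4.5 h who meet the remaining criteria. The conclusion assumes that the patient was symptom-free when sleep began, as section 5.1 requires, and that no site procedure outside the documents already diverts such patients.

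Two stronger readings should be resisted. A reader might infer a number of good outcomes lost from the 9-point benefit in section 11.1 of the older version or the 10-point benefit in the current section 11.1. The first comes from a superseded calculation, is tied to a common odds ratio and is set beside a good outcome of mRS 0-2. The second is for mRS 0-1 and is the trial's own hypothesis. Neither estimates the benefit in short sleepers, and with no frequency available no such count should be claimed. A reader might also infer that the primary estimate or the target of 600 is compromised. Nothing in the documents shows that, and neither is at issue here.

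**What to change.** **Now:** remind sites that a patient who can be treated within 4.5 hours of the time last known free of symptoms should be considered for standard thrombolysis rather than randomised. This does not have to wait for the amendment.

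**At the next amendment:** add to section 5.2 an exclusion such as *Patient can be treated within 4.5 hours of the time last known free of symptoms and is eligible for thrombolysis under local standard care.* If the randomisation form does not already record that time, add the field so that the check in section 12.7 can apply the rule. No extra analysis is needed.

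**Cost:** one line, at most one form field, and a few fewer eligible patients. Under section 12.8 the change needs Steering Committee approval and then approval by competent authorities and ethics committees, across the ten countries named in section 2. That is a reason to bundle it rather than amend for this alone. Section 17 lists changes to section 5.2 in 4 of 7 versions (160323, 180410, 180704, 200917), so bundling is realistic. Last inclusion is planned for September 2021, about 12 months after version 200917. Approval time uses up part of that period, and the exclusion protects only patients not yet randomised, which is why the reminder should come first.

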## 5.2 Exclusion criteria

- Age <18 years
- NIHSS score >25 or NIHSS consciousness score >2, or seizures during stroke onset
- Findings on non-contrast CT that indicate that the patient is unlikely to benefit from treatment:
  - Infarction comprising more than >1/3 of the middle cerebral artery territory on non-contrast CT or CT perfusion
  - Intracranial haemorrhage, structural brain lesions which can mimic stroke (e.g cerebral tumour)
- Active internal bleeding of high risk of bleeding, e.g.:
  - Major surgery, trauma or gastrointestinal or urinary tract haemorrhage within the previous 21 days, or arterial puncture at a non-compressible site within the previous 7 days
  - Any known defect in coagulation, e.g. current use of vitamin K antagonist with an INR >1.7 or prothrombin time >15 seconds, or use of direct thrombin inhibitors or direct factor Xa inhibitors during the last 24 hours (unless reversal of effect can be achieved by agents such as idarusizumab) or with elevated sensitive laboratory tests (such as aPTT, INR, platelet count, eucarin clotting time, TT, or appropriate factor Xa activity assays), or heparins during the last 24 hours or with an elevated aPTT greater than the upper limit of normal
  - Known defect of clotting or platelet function or platelet count below 100,000/mm^3 (but patients on antiplatelet agents can be included)
  - Ischaemic stroke or myocardial infarction in previous 3 months, previous intracranial haemorrhage, severe traumatic brain injury or intracranial or intraspinal operation in previous 3 months, or known intracranial neoplasm, arteriovenous malformation or aneurysm
- Contraindications to tenecteplase, e.g., acute bacterial endocarditis or pericarditis; acute pancreatitis; severe hepatic dysfunction, including hepatic failure, cirrhosis, portal hypertension; active hepatitis; systemic cancer with increased bleeding risk; haemostatic defect including secondary to severe hepatic, renal disease; organ biopsy; prolonged cardiopulmonary resuscitation > 2 min (within 2 weeks)
- Persistent blood pressure elevation (systolic  $\geq$ 185 mmHg or diastolic  $\geq$ 110 mmHg), despite blood pressure lowering treatment
- Blood glucose <2.7 or >20.0 mmol/L (use of finger-stick measurement devices is acceptable)
- Pregnancy, positive pregnancy test, childbirth during last 10 days, or breastfeeding. In any woman of childbearing potential, a pregnancy test must be performed and the result assessed before trial entry
- Other serious or life-threatening disease before the stroke: severe mental or physical disability (e.g. Mini Mental Status score <20, or mRS score  $\geq$ 3), or life expectancy less than 12 months
- Patient unavailability for follow-up (e.g. no fixed address)

